5.4 Missing Data

In general, missing data will not be imputed unless specified in this document. Handling of missing data in the efficacy analyses are described separately in Section 12.3.

5.4.1 Missing or Incomplete Date for Last Dose of Study Drug

The missing last dose date of study drug for a subject who completed or early terminated from the study will be imputed using the last expected dosing date, which is defined as the minimum of the non-missing drug return date of the last dispensed drug kits, the last drug dispensed date plus the number of days that the dosing would continue per protocol or the end-of-treatment/early termination visit (EOT/ET) date, whichever occurs earlier. For the incomplete last dose date of the study drug, the imputation will be compared against the last expected dosing date defined as above. Details will be provided in a separate specifications document. The missing or incomplete dates will be displayed in the data listings as reported on the eCRF rather than the imputed dates.

For data summarization before final database lock, if a subject is still ongoing at the time of analysis, then this subject's last dose date will be imputed using the database extract date.

5.4.2 Missing or Incomplete Dates for Prior or Concomitant Medications

Missing or incomplete medication start or end dates will be imputed for the purpose of determining whether the medications are taken concomitantly (see Section 11 for definition). When the chronological order of medication use relative to the study drug treatment period is unclear due to missing or incomplete date(s), the medication will be considered as concomitant. The imputation algorithms will be provided in a separate specifications document. The missing or incomplete dates will be displayed in the data listings as reported on the eCRF rather than the imputed dates.

5.4.3 Missing or Incomplete Dates for Adverse Events

Missing or incomplete adverse event (AE) start dates will be imputed for the purpose of determining whether the AEs are treatment-emergent (see Section 14.1 for definition). When the chronological order of an AE onset relative to the study drug treatment period is unclear due to missing or incomplete date(s), the AE will be considered as treatment-emergent. The imputation algorithms will be provided in a separate specifications document. The missing or incomplete dates will be displayed in the data listings as reported on the eCRF rather than the imputed dates.

5.4.4 Missing Severity Assessment for Adverse Events

If the severity is missing for an AE starting on or after the date of the first dose of study drug, then a severity of "Severe" will be assigned. The imputed values for severity assessment will be used for incidence summaries, and the actual values will be presented in data listings.

5.4.5 Missing Relationship to Study Drug for Adverse Events

If the relationship to study drug is missing for an AE starting on or after the date of the first dose of study drug, a causality of "Related" will be assigned. The imputed values for relationship to study drug will be used for incidence summaries, and the actual values will be presented in data listings.

5.5 Character Values of Clinical Laboratory Variables

If the reported value of a clinical laboratory variable cannot be used in a statistical analysis due to, for example, a character string reported for a numeric variable, an appropriately determined coded value will be used in the statistical analysis. The coding algorithms will be provided in a separate specifications document. The actual values as reported in the database will be presented in data listings.

6 SUBJECT DISPOSITION

For subjects who participate in the screening phase but are not randomized (screen failures), their demographics information (including age, sex, and primary race), screen failure reasons (the

specific inclusion/exclusion criterion (or criteria) not met or other reason including the reason due to coronavirus disease 2019 [COVID-19]) and protocol version will be provided in a listing. If a subject is re-screened, then the re-screening subject ID and the final enrollment status (whether eventually enrolled) will also be displayed in this listing. In addition, the frequency that the screen failure reasons are reported will also be summarized. Note that one subject may be deemed ineligible for multiple inclusion/exclusion criteria. A single rescreening of individuals who fail screening is permitted with the approval of the Sponsor's Medical Monitor.

The number of sites that screened at least one subject, number of sites that randomized at least one subject, number of subjects screened, number of unique subjects screened, and number of randomized subjects will be summarized.

For randomized subjects, number and percentage of subjects in Safety Analysis Set, Full Analysis Set, and PK Analysis Set will be summarized by treatment group and overall. A listing will be provided displaying all subjects excluded from the Safety or Full Analysis Sets, and will include reason(s) for exclusion.

In addition, the number of subjects randomized at each site will also be tabulated by Analysis Set and by treatment group and overall.

For Randomized Analysis Set and Full Analysis Set, the number and percentage of subjects who completed the study or discontinued (all discontinued and by primary discontinuation reason including the reason due to COVID-19) will also be summarized by treatment group and overall. A listing will be provided on the reasons for premature study drug/study discontinuation.

7 PROTOCOL DEVIATIONS

Protocol deviations will be reviewed regularly over the course of the study. The review process, definition of the deviation categories, and the classification of a deviation as major or minor are detailed in the Protocol Deviation Management Plan. Protocol deviations will also be assessed with respect to relationship to COVID-19.

A summary of the number and percentage of subjects with major protocol deviations for each deviation category will be presented by treatment group and overall in three ways: all protocol deviations, COVID-19 related protocol deviations, and non COVID-19 related protocol deviations.

Two listings of protocol deviations will be provided: all deviations and COVID-19 related protocol deviations.

8 DEMOGRAPHICS AND OTHER BASELINE CHARACTERISTICS

8.1 Demographics and Other Baseline Characteristics

Demographics and baseline characteristics will be summarized by treatment group and overall, for Randomized Analysis Set and Full Analysis Sets using descriptive statistics. Variables include age, age category (5-12 years and 13-17 years), mental age, sex, primary race (subjects of multi-racial background can only identify/select one primary race on eCRF, or choose "other" and specify), ethnicity, height, weight, body mass index (BMI), intelligence quotient (IQ), IQ categories (<70 and \geq 70), region, and caregiver relationship.

The reported age reflects a subject's age at the informed consent date. Age will be presented both as continuous and categorical (5 through 12 years old or 13 through 17 years old). If there are discrepancies in the values between the IRT system and the clinical database, categories based on the IRT system and clinical database will each be presented separately.

8.2 Baseline Disease Characteristics

Disease characteristics at Baseline will be summarized for the Randomized Analysis Set and Full Analysis Set using descriptive statistics. Baseline ABC subscale scores, CGI-S of irritability score, RBS-R score, VABS-Socialization score, CGSQ score, ADI-R, MINI-KID, and ESRS-A score will be presented as continuous variables. CGI-S of irritability score will also be presented as a categorical variable using discrete categories. Subject history of syncope, family history of syncope, subject history of somnolence will be summarized using yes/no counts.

9 MEDICAL HISTORY

Medical and surgical history data will be coded using Medical Dictionary for Regulatory activities (MedDRA) version 24.0 or higher. The subject incidence will be summarized for each system organ class (SOC) and preferred term by treatment group and overall, for Safety Analysis Set. A subject will be counted only once per SOC or per preferred term for the summary.

A listing of the SOC, preferred term, body system, verbatim term for the medical history condition/event, start and stop dates (when available), and an indicator for whether or not the condition is ongoing will be provided.

10 EXTENT OF EXPOSURE AND TREATMENT COMPLIANCE

Summaries of exposure and compliance to study drug will be provided for the Safety Analysis Set.

10.1 Exposure to Study drug

For each subject, the duration of exposure to study drug (last dose date – first dose date + 1), will be calculated and summarized by treatment group. Duration of exposure will also be summarized with number and percentage of subjects in each of the following categories: <1 week (1 to 7 days), 1 to <2 weeks (8 to 14 days), 2 to <3 weeks (15 to 21 days), 3 to <4 weeks (22 to 28 days), 4 to <5 weeks (29 to 35 days), 5 to <6 weeks (36 to 42 days), and \geq 6 weeks (43 days or longer).

The pimavanserin dose levels are expressed as free base.

10.2 Measurement of Treatment Compliance

Study drug dosing compliance (in percentage) for a subject is defined as the total number of capsules actually taken divided by the number of capsules expected to be taken and then multiplied by 100. The total number of capsules actually taken is calculated by the total number of capsules dispensed minus the total number of capsules returned. The number of capsules expected to be taken is calculated as the duration of exposure (days) × 1 (number of tablets taken per day). Additional details for handling missing number of capsules returned will be provided in a separate specification document.

Compliance will be summarized as both continuous and categorical variables by treatment groups. For categorical presentation, the number and percentage of subjects in each of the following categories will be presented: <80%, 80 to 120%, and >120%.

Listings of study drug accountability will be provided separately.

11 PRIOR, CONCOMITANT AND POST-TREATMENT MEDICATION

For a subject, prior medication is defined as any medication with stop date prior to the date of the first dose of study drug. Concomitant medication is defined as any medication that is ongoing at the first dose of study drug or with a start date between the dates of the first and last doses of study drug, inclusive. Any medication with a start date after the date of the last dose of study drug will be considered as post-treatment medication. Prior, concomitant, or post-treatment medications will be summarized separately. Medications will be coded using WHO Drug Dictionary 2021 March or newer version. The number and percentage of subjects taking each drug class (ATC Level 3) and medication preferred term will be tabulated by treatment group and overall, for Safety Analysis Set. Multiple medication usage by a subject in the same category will be counted only once.

Relationship to COVID-19 will be assessed for selected medications as detailed in the Guidance for Site Documentation and Data Management Querying of Data Impacted by COVID-19 (GSD)

and provided in a listing. Listings of the prior, concomitant, or post-treatment medications will be provided.

12 EFFICACY ANALYSIS CONSIDERATIONS

All efficacy analyses will be performed using the planned treatment assignments based on the randomization schedule for the Full Analysis Set.

12.1 Efficacy Variables

Primary Efficacy Endpoint

The primary efficacy endpoint is the change from Baseline at Week 6 in the ABC-I score.

Secondary Efficacy Endpoints

The secondary efficacy endpoints are the following:

- Change from Baseline at Week 6 in the caregiver-rated ABC subscale scores
 - o Stereotypic behavior
 - o Lethargy
 - Hyperactivity
 - o Inappropriate speech
- Change from Baseline at Week 6 in the Clinical Global Impression–Severity (CGI-S) of irritability score
- Clinical Global Impression–Improvement (CGI-I) of irritability score at Week 6
- Change from Baseline at Week 6 in the Repetitive Behavior Scale–Revised (RBS-R) scores
- Change from Baseline at Week 6 in the Vineland Adaptive Behavior Scales (VABS)—Socialization subscale score
- Change from Baseline at Week 6 in the Caregiver Strain Questionnaire (CGSQ) Since last visit scores
- Proportion of subjects who have at least 25% reduction from Baseline in the ABC Irritability subscale score at Week 6
- Proportion of subjects who have CGI-I of irritability score of 1 (very much improved) or 2 (much improved) at Week 6 (CGI-I of irritability responders)
- Proportion of subjects who have at least 25% reduction from Baseline in the ABC Irritability subscale score AND a CGI-I of irritability score of 1 (very much improved) or 2 (much improved) at Week 6

12.2 Adjustment for Covariates

For continuous variables analyzed using the mixed model for repeated measures (MMRM), the stratification factors (age group and region) and the baseline value of the endpoint being analyzed will be included as covariates as described in Section 13. For CGI-I of irritability score, the Baseline CGI-S of irritability score will be included in the MMRM analysis.

12.3 Handling of Missing Data

The primary analysis of the primary efficacy variable will be performed assuming missing at random (MAR) using an MMRM method. ABC-I scores that are missing (based on approaches described in Section 5.2.1) will not be imputed. The MMRM method is unbiased in the estimation of treatment effect under the MAR assumption and can be thought of as aiming to estimate the treatment effect that could have been observed if all subjects had continued on treatment for the protocol planned treatment duration (EMA, 2009). Sensitivity analyses of the primary efficacy variable will be performed as described in Section 13.

12.4 Multiple Comparisons / Multiplicity

A hierarchical testing procedure will be used to control the Type I error rate across the two treatment comparisons (pimavanserin high dose vs. placebo and pimavanserin low dose vs. placebo) for the primary endpoint and an important secondary endpoint CGI-S. The hypotheses testing will be conducted in sequential order:

- 1. pimavanserin high dose versus placebo on change from Baseline to Week 6 ABC-I score
- 2. pimavanserin low dose versus placebo on change from Baseline to Week 6 ABC-I score
- 3. pimavanserin high dose versus placebo on change from Baseline to Week 6 CGI-S score
- 4. pimavanserin low dose versus placebo on change from Baseline to Week 6 CGI-S score

If the proceeding comparison fails to reach statistical significance at the 2-sided 0.05 level, the subsequent comparison(s) will be declared as not statistically significant regardless of the associated nominal p-value. The study-wise Type I error rate will be maintained at the significance level of 0.05.

No statistical inference will be made for any other secondary endpoints.

12.5 Examination of Subgroups

Treatment comparisons will be made with respect to the primary efficacy variable using the MMRM analysis described in Section 13.1.1 separately for each subgroup by:

• age group (5 through 12 years old or 13 through 17 years old)

- Only the region stratification factor (U.S. or rest of world) will be included in the MMRM model for this analysis
- sex (male or female)
- primary race (white or non-white)
- IQ ($<70 \text{ or } \ge 70$)
- region (U.S.A. or rest of world)
 - Only the age group stratification factor (5 through 12 years old or 13 through 17 years old) will be included in the MMRM model for this analysis
- severity of ABC-I at entry (<25 or ≥ 25)
- severity of ABC-Lethargy at entry (ABC-L) (<20 or ≥20)
- stimulants (defined as ATC level 3 = 'PSYCHOSTIMULANTS, AGENTS USED FOR ADHD AND NOOTROPICS') use during treatment period (yes or no)

The LS mean differences with corresponding 95% CIs from the subgroups will also be graphically presented in forest plots for the primary efficacy variable.

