16. Female subjects who participate in this study must either be unable to become pregnant (e.g., premenarchal, surgically sterile, etc.) -OR- agree to use a highly effective non-hormonal method of contraception (e.g., intrauterine device, condom or diaphragm with spermicides, or contraceptive sponge) from 28 days before Baseline to 45 days after last dose (if subject does not roll over into the open-label extension study).

Females of childbearing potential must have a negative serum human chorionic gonadotropin (hCG) pregnancy test at Screening and a negative urine hCG pregnancy test at Baseline. Females of childbearing potential are defined as females who have begun menstruating.

4.2 **Exclusion Criteria**

A subject must meet none of the following exclusion criteria to be eligible for the study:

Central Nervous System, Psychiatric, and Illicit Drug Use Criteria

1. Requires treatment with a medication prohibited by the protocol, including concomitant psychotropic drugs targeting irritability, including those used off-label (clonidine, guanfacine, and propranolol; lithium, valproate), medications that prolong the QT interval, and strong cytochrome P450 (CYP) 3A4 enzyme (CYP3A4) inhibitors and inducers (see Appendix A and Appendix B)

Final Version: 1.0

2. Subjects who have had changes in medications or medication doses (for medical and allowed comorbid psychiatric conditions) within 4 weeks of Baseline

- 3. Any history as reported by the caregiver or documented by medical records, when available, of angioedema, serotonin or neuroleptic malignant syndromes, dystonic reaction, or tardive dyskinesia, due to an antipsychotic or psychotropic medication.
- 4. Is at a significant risk of suicide, or is a danger to self or others, in the opinion of the Investigator based upon all available sources of information including C-SSRS (positive answer to suicidal ideation questions 4 or 5 [current or over last 6 months]) at Screening or Baseline and including more than one life-threatening suicide attempt (positive answer to suicidal behavior questions [over last 6 months])
- 5. Is at risk of significant violent behavior to the extent that participation would pose an undue risk to other patients, caregivers, or others in the opinion of the Investigator

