4.8.2.1 Permitted, Restricted, and Prohibited Medications

Prohibitions and restrictions for concomitant medications should be followed between the initial screening visit and Visit 8 (EOT)/ET as specified in Appendix A and Appendix B. These appendices do not constitute an exhaustive list and any questions regarding prohibited and restricted medications should be discussed with the Medical Monitor or designee. The Investigator may prescribe appropriate medication to treat AEs.

Medications that can prolong QT interval are prohibited (or restricted) as specified in Appendix A.

Permitted concomitant medications should remain at a stable dose throughout the treatment period.

If a subject is on a medication restricted by the protocol, the medication should be adjusted if it is determined by the Investigator to be clinically appropriate (e.g., if the subject's symptoms are not well-controlled or if the subject cannot tolerate the current medication) in consultation with the treating physician.

Subjects who require current treatment with a prohibited medication will be withdrawn from the study.

Subjects who have taken a prohibited medication during the study will be withdrawn from the study unless:

- the prohibited medication has been discontinued, AND
- withdrawal from the study presents an unacceptable medical risk to the subject

The justification to allow the subject who has taken a prohibited medication to continue in the trial will be made by the Sponsor/Medical Monitor with medical input from the Investigator, and will be documented. If a subject is allowed to remain in the trial, this will be reported as a major protocol deviation and not a waiver.

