	RESTRICTED alprazolam lorazepam midazolam oxazepam temazepam triazolam	• Mild sedation is allowed exceptionally for ECGs and blood draws during the study (e.g., alprazolam at a pediatric-appropriate dose per age, and the lowest dose deemed necessary by the Investigator) just in cases when the subject's agitation/anxiety does not allow a safe and accurate measurement and the Investigator, with agreement from the caregiver, considers it safe and appropriate for the subject.

Final Version: 1.0 Date: 21 December 2022

Medication Class	Medicationa	Prohibition/restrictions
		 Short- or medium-acting benzodiazepine may be used for acute anxiety May not be used within 12 hours prior to an assessment visit Lorazepam, in doses according to age, may be used as a rescue medication for a maximum of 7 consecutive days. Reassessment and discussion with Medical Monitor is required if needed beyond 7 days. If lorazepam is not available, another benzodiazepine from the restricted list may be used
Beta blockers	PROHIBITED • propranolol	Prohibited at study entry and throughout the treatment period
Centrally-acting alpha-agonist hypotensive agents	PROHIBITED • clonidine	Prohibited at study entry and throughout the treatment period
Centrally-acting alpha _{2A} adrenergic receptor agonists	PROHIBITED • guanfacine	Prohibited at study entry and throughout the treatment period
Hypnotics and sleeping agents	PROHIBITEDeszopiclonezolpidemzopiclone	Prohibited at study entry and throughout the treatment period
	RESTRICTED • melatonin • ramelteon • zaleplon	May not be used within 12 hours of a cognitive assessment, and efforts should be made to limit agents to lowest dose for the shortest time needed. ○ Melatonin is allowed (≤5 mg/day) for insomnia
Non-stimulant ADHD medications	RESTRICTED • atomoxetine	Allowed if stable for at least 12 weeks prior to Screening and the dose is expected to remain the same throughout the duration of the study
Opioids	PROHIBITED • methadone	Prohibited at study entry and throughout the treatment period
Serotonin antagonists	PROHIBITED • cyproheptadine	 Prohibited throughout the treatment period Must be discontinued at least 3 weeks prior to the Baseline visit
Stimulants and wake-promoting agents	RESTRICTEDamphetamine saltsarmodafinil	Allowed if stable for at least 12 weeks prior to Screening and the dose is expected to remain the same throughout the duration of the study

Final Version: 1.0 Date: 21 December 2022

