14.1 Adverse Events

All Adverse events (AEs) will be coded using MedDRA version 24.0 or higher.

An AE (classified by preferred term) will be considered a treatment-emergent AE (TEAE) if it starts after the first study dose administration and no later than last study dose date + 30 days. AEs reported on Day 1 based on Baseline (pre-dose) findings (e.g. clinically significantly abnormal vital signs, laboratory test results, or electrocardiogram parameters) will not be considered as TEAEs.

The event counts and the number and percentage of subjects reporting TEAEs in each treatment group, and the two pimavanserin groups combined will be tabulated by SOC and preferred term; and, by SOC, preferred term, and maximum severity. If more than one AE occurs with the same preferred term for the same subject, the subject will be counted only once for that preferred term using the most severe and more related occurrence for the summarization by severity and by relationship to study drug, respectively. The display in these tables will be sorted alphabetically by SOC, and then by frequency of the two pimavanserin groups combined within each SOC.

The event counts and the number and percentage of subjects with any TEAEs will also be tabulated by preferred term without SOCs within each treatment group and sorted by frequency of the two pimavanserin groups combined.

The incidence of most frequently reported (preferred terms reported by $\geq 5\%$ of subjects in any treatment group) TEAEs, TEAEs leading to discontinuation, TEAEs related to study drug, TEAEs by maximum severity, fatal TEAEs (i.e., events that cause death), serious TEAEs, and serious TEAEs related to study drug, will be summarized by SOC, preferred term, and treatment group. In addition, TEAEs by SOC, preferred term, and stimulant use will be summarized.

Version 3.0

29 July 2024

The relationship of selected AEs to COVID-19 will be assessed as detailed in the GSD and provided in the listing. Additional summaries of relationship to COVID-19 may be provided.

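### The SAP's stimulant subgroup is classified by use after randomisation and by a drug class broader than its label; any bias is probably small, and a baseline definition with an explicit drug list or an accurate name would fix it.

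*SAP*

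**What the plan says.** SAP Section 12.5 repeats the primary "MMRM analysis described in Section 13.1.1 separately for each subgroup by" a list of factors: age group, sex, race, IQ, region, severity of ABC-Irritability at entry, severity of ABC-Lethargy at entry, and stimulants. The stimulants factor is the ATC level 3 class "PSYCHOSTIMULANTS, AGENTS USED FOR ADHD AND NOOTROPICS", classified by "use during treatment period (yes or no". The results feed a forest plot. SAP Section 21.4 dates this subgroup to version 3.0 (29 July 2024), and the later addendum does not change it.

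SAP Section 14.1 adds that "TEAEs by SOC, preferred term, and stimulant use will be summarized". It does not define stimulant use.

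SAP Section 11 treats a drug as concomitant if it is ongoing at the first dose or starts between the first and last doses.

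Protocol Appendix A puts atomoxetine in a row called "Non-stimulant ADHD medications". A separate row for stimulants and wake-promoting agents names amphetamine salts, armodafinil, lisdexamfetamine, methylphenidate and modafinil. Both rows carry the same condition: "Allowed if stable for at least 12 weeks prior to Screening and the dose is expected to remain the same". Exclusion criterion 2 (Protocol Section 4.2) excludes "Subjects who have had changes in medications or medication doses (for medical and allowed comorbid psychiatric conditions) within 4 weeks of Baseline". Protocol Section 4.8.2.1 adds: "Permitted concomitant medications should remain at a stable dose throughout the treatment period".

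**The concern.** Two features of the definition do not fit its purpose.

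First, timing. A subgroup factor should be known before treatment can influence it. Use during treatment is observed after randomisation, so a subject who does badly and is started on such a drug can enter the user group because of the outcome under study. If starts differ by arm, the comparison within each subgroup is no longer between randomised groups.

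Second, content. The factor is called stimulants, but the class name also covers ADHD agents and nootropics. A compliant subject whose only such drug is atomoxetine would probably be reported as a stimulant user, although the protocol calls that drug non-stimulant.

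At stake is how one row of the efficacy forest plot is read, and possibly how the adverse-event split is read.

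**Working it through.** **1. Label against content.** The inputs are the class name in SAP 12.5 and the two rows in Protocol Appendix A. The class name includes agents used for ADHD and SAP 12.5 makes no exception. Atomoxetine is an ADHD drug that the protocol permits and does not call a stimulant. So the class is broader than the label, and this needs no protocol deviation. The step from class name to atomoxetine's actual code is an inference.

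**2. Who can change group.** Compare use ongoing at first dose with use during treatment, read with the SAP Section 11 definition:

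| Subject | At first dose | During treatment |
|---|---|---|
| User throughout | Yes | Yes |
| User who stops after the first dose | Yes | Yes |
| User who adds a second drug of the class | Yes | Yes |
| Non-user who never starts | No | No |
| Non-user who starts on treatment | No | **Yes** |

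Only the last row differs. Under the Appendix A condition, such a start departs from the protocol.

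**3. The plan's own figure.** The documents give no figure for this subgroup, but the sample-size section supplies the scale. A two-sided, two-sample t-test with difference 5, SD 10 and alpha 0.05 has power 0.801 at 64 per arm. Then 64 / (1 − 0.15) = 75.3, rounded up to 76, and 3 × 76 = 228. The plan's numbers reproduce.

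**4. Possible bias, under assumptions.** Suppose there is no true effect, SD is 10 and 20% are baseline users. New starts occur only among baseline non-users in the worse-scoring half, with probability s. That half has a mean 10 × √(2/π) = 7.98 points above average. In one arm:

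- mean among users = 0.4s × 7.98 / (0.2 + 0.4s)
- mean among non-users = −0.4s × 7.98 / (0.8 − 0.4s)

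Here 0.4 = 0.8 × 0.5. With s = 0.10 on placebo and 0.05 on active:

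- users: placebo 0.04 × 7.98 / 0.24 = 1.33; active 0.02 × 7.98 / 0.22 = 0.73; active minus placebo about −0.6
- non-users: placebo −0.04 × 7.98 / 0.76 = −0.42; active −0.02 × 7.98 / 0.78 = −0.20; active minus placebo about +0.2

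With 0.10 against 0.02, the differences are about −1.0 and +0.3. With equal rates (0.05 and 0.05), or with no starts, they are zero. A simulation of the same set-up agreed (−0.61 and +0.22; −0.99 and +0.34; zero within simulation error). Negative values favour active treatment.

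**5. Set against the precision available.** The 95% half-width for a difference among users is 1.96 × 10 × √(2/m), with m users per arm out of 64 evaluable:

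| Assumed share of users | m | Half-width (points) | Power for 5 points |
|---|---|---|---|
| 10% | 6 | 11.3 | 12% |
| 20% | 13 | 7.7 | 23% |
| 30% | 19 | 6.4 | 32% |
| 50% | 32 | 4.9 | 50% |

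At the 20% share used in step 4, a bias of 0.6 to 1.0 points compares with a half-width of 7.7.

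**The case against.** The best defence is that the stability rules make the two time windows coincide. In a compliant subject, use during treatment is use at Baseline, so the post-randomisation wording matters only for deviators, and then biases the comparison only if starts depend on outcome and differ by arm. The documents give no sign of how often that would happen. This stands, and it limits the size of the problem. It also means that the later window gains nothing.

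The definition is also prespecified, reproducible and printed beside its label, using the ATC level 3 coding that SAP Section 11 applies to all medications. That is fair: a dictionary class is a legitimate choice if it is named for what it contains. For adverse events, grouping by concurrent exposure is defensible too.

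Three stronger readings are tempting but not supported:

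- A reader might infer that any drug started or added after randomisation moves a subject between groups. The table in step 2 shows that an existing user stays a user.
- A reader might infer that the adverse-event table is mislabelled as well. Section 14.1 gives no definition, so that cannot be established; the gap is the missing definition.
- A reader might put a number on misclassification. Assuming that 20–30% take an ADHD drug and 10–30% of those take atomoxetine gives 228 × 0.20 × 0.10 = 4.6 to 228 × 0.30 × 0.30 = 20.5 subjects. Neither share comes from the documents, and anyone also taking a stimulant would be classified correctly.

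**Conclusion.** The point holds as a matter of definition and is minor. As written, the factor is post-randomisation and broader than its name. The breadth affects compliant subjects, but the link to atomoxetine rests on the class name and the number affected is unknown. The timing affects only baseline non-users who start such a drug on treatment. The resulting bias is zero without such starts and was about 0.6 to 1.0 points in users under the unequal start rates assumed above.

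No controlled conclusion changes. The subgroup is outside the hierarchical procedure, both in SAP Section 12.4 and as restored by the addendum, and SAP Section 14 specifies descriptive safety summaries with no formal testing. The primary analysis is unaffected.

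**What to change.** In SAP Section 12.5, classify subjects by use ongoing at the first dose. For content, do one of two things:

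- use an explicit, prespecified list of stimulants consistent with Appendix A, with atomoxetine kept separate; or
- keep the ATC class and rename the factor ADHD/psychostimulant medication use at Baseline.

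The list cannot simply point to the Appendix A row. That row also covers wake-promoting agents, and the table's footnote says its examples are not exhaustive, so the list must settle both matters. State in SAP Section 14.1 that the adverse-event split uses the same definition. A version based on use during treatment can be kept as supplementary.

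The cost is a wording change and, under the first option, a short drug list to finalise before unblinding. The medication data needed are already collected.
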